7.8.3 Vital signs

Descriptive summaries of vital signs and body weight values over time and for the difference from baseline will be provided.

Clinically relevant findings in vital signs data will be reported as AEs and will be analyzed as part of AE analyses.

7.8.4 ECG

All evaluations of ECG data will be based on data from the ECGS.

For quantitative endpoints, listings of individual data with notable findings flagged will be provided in Appendix 16.2. For patients with any notable finding in quantitative ECG recordings, a separate listing with corresponding time profiles will be created as an end-of-text display.

Comments regarding the ECG recordings will be provided in a listing.

For categorical ECG endpoints, frequency tables will be provided. Findings of ECG abnormalities from morphological analyses will also be analyzed as categorical endpoints.

Descriptive statistics (N, mean, SD, min, median, max) will be provided for absolute values of QTcF, HR, QT, PR and QRS. Changes from baseline over time will also be presented for these values. Time profiles of mean and SD of change from baseline while on treatment will be displayed graphically by treatment.

To evaluate the appropriateness of the heart rate correction methods, the slope of the relationship of QTcF interval versus RR interval (values log-transformed using the natural logarithm) will be estimated by applying the random coefficient model described in [Section 9.1.1](#) using all time points. A scatterplot of QTcF vs RR including the overall regression line will be included in the Statistical Appendix of the CTR. The resulting (fixed effect) slope together with two-sided 95% confidence intervals will be included in the footnote for this plot.

[figure not shown]

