### 7.3.4 Safety analyses

All findings noticed at ophthalmological examinations and/or clinically relevant symptoms (according to the judgment of the investigator) which are reported by the patients will be recorded as ocular adverse events according to the CTCAE classification. All adverse events will be coded using the Medical Dictionary for Drug Regulatory Activities (MedDRA).

Standard BI summary tables and listings will be produced. Consistent with the REP definition in [Section 5.2.6.2.1](#), all adverse events with an onset between start of treatment and last follow up visit will be assigned to the on-treatment period for evaluation. Measurements (such as ECG, vital signs, or laboratory parameters) or AEs will be assigned to treatments (see [Section 4.1](#)) based on the actual treatment at the planned time of the measurement or on the recorded time of AE onset (concept of treatment emergent AEs). Therefore, measurements planned or AEs recorded prior to first intake of trial medication will be assigned to 'screening' and those between first trial medication intake until the last follow up visit will be assigned to the treatment period. These assignments including the corresponding time intervals will be defined in detail in the TSAP.

All treated patients will be included in the safety analysis. In general, safety analyses will be descriptive in nature and will be based on BI standards. No hypothesis testing is planned.

Statistical analysis and reporting of adverse events will concentrate on treatment-emergent adverse events, i.e. all adverse events occurring between start of treatment and last follow up visit. Adverse events that start before first drug intake and deteriorate under treatment will also be considered as 'treatment-emergent'.

Frequency, severity, and causal relationship of adverse events will be tabulated by system organ class and preferred term after coding according to the current version of the Medical Dictionary for Drug Regulatory Activities (MedDRA) at the database lock. This also includes the primary endpoint.

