6.3 PATIENT SETS ANALYSED

The following patient analysis sets are defined for this trial:

- Screened set (SS): includes all patients who sign informed consent
- Randomized set (RS): includes all patients who sign informed consent, are screened for the trial and are randomized to trial medication, regardless of whether any trial medication is administered.
- Treated set (TS): includes all patients who sign informed consent, are dispensed trial medication and are documented to have taken at least one dose of trial medication (BI 1467335 or placebo). Safety analyses, including the analyses of the primary endpoint of ocular adverse events and secondary endpoint of non-ocular adverse events, and summaries of demographics and baseline characteristics will be based on the TS.
- Full analysis set (FAS): includes all patients in the TS with non-missing baseline and at least one non-missing on-treatment measurement for DRSS or BVCA. Patients in

FAS are analyzed according to the intent-to-treat principle, i.e. patients in FAS are analyzed according to the trial medication assigned at randomization.

- Per protocol set (PPS): includes all patients from the FAS who do not have an iPD resulting in exclusion from the PPS.
- [REDACTED]
- ECG analysis set (ECGS): includes all subjects in TS who have at least one baseline and one post-baseline measurement for at least one ECG interval endpoint.

Analyses relevant to each patient set are shown in [Table 6.3: 1](#).

Table 6.3: 1 Patient sets analyzed

Class of endpoint	Patient set					
	SS	RS	TS	FAS	PPS	[REDACTED]
Primary and secondary safety endpoints			X			
Secondary ophthalmologic endpoint				X	X	
Further ophthalmic endpoints				X		
Safety endpoints			X			
[REDACTED]						[REDACTED]
ECG endpoints						X
Demographic/baseline endpoints			X			
Important protocol deviations		X				
Disposition	X					

[REDACTED]

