6.6 HANDLING OF MISSING DATA AND OUTLIERS

Techniques for handling missing data are described in Section 7.5 of the CTP. Missing and incomplete adverse event dates will be handled according to BI standards (5). The handling of missing PK data and values reported as NOS, NOR, NOA or BLQ are described in Section 10.1 of the CTP.

For efficacy analyses, missing data will not be imputed. Mixed effect models will handle missing data based on a likelihood methods under the “missing at random” assumption. No imputations of missing AEs, laboratory data or vital signs data are planned. For binary efficacy endpoints, patients with missing data in the study eye at the time point of interest will be considered non-responders, i.e. failure to achieve the defined endpoint.

For ECG data, if single cardiac cycles of an ECG (out of three) are missing, the arithmetic mean for this single ECG will be calculated with the reduced number (1 or 2) of cycles.

For the classification of the on-treatment QTc/QT intervals into ‘no new onset’ / ‘new onset’ categories, a missing value is obtained only in the case that

- i. all on-treatment values are missing, and
- ii. the baseline value is less than or equal to 500 msec, or missing.

If condition (i) is fulfilled but the baseline value is greater than 500 msec, this case will be categorized as ‘no new onset’. If baseline is missing and the maximum on-treatment QTc interval is greater than 450 msec (or 500 msec for QT interval, respectively), this is classified as a ‘new onset’ in the respective category. If baseline is missing and the maximum QTc interval is less than or equal to 450 msec (or 500 msec for QT interval, respectively), this will be categorized as ‘no new onset’. If baseline is missing, a QTc/QT interval > 500 msec at any time on treatment will be a notable finding.

For patients on active drug, missing plasma concentration values with ‘BLQ’ in the comment field will be replaced by $\frac{1}{2}$ LLOQ.

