FU3	EOT + 84	Date of drug intake in EOT visit +63	Last assessment date	Follow-up 3

b Day 1 is defined as the date of first treatment administration

c Baseline data must be collected before time of study drug administration during Visit 2.

Table 6.7: 2 Visit intervals for ECG, vital signs, and laboratory data

		Interval Definition		
Visit	Planned day	From (day)	To (day)	Visit description
1	-28 to -3	NA	-1	Screening ^a
2a	1	1 ^b (pre-dose)	1	Baseline ^{a,c}
2a	1	1 (post-dose)	14	Week 1 ^d
3	29	15	43	Week 4
4a	57	44	71	Week 8
EOT	85	72	Date of drug intake in EOT visit +1	Week 12
FU1	EOT +28	Date of drug intake in EOT visit +2	Date of drug intake in EOT visit +34	Follow-up 1 ^e
FU2	EOT +56	Date of drug intake in EOT visit +35	Date of drug intake in EOT visit +62	Follow-up 2
FU3	EOT + 84	Date of drug intake in EOT visit +63	Last assessment date	Follow-up 3

a Baseline ECG data are collected at screening visit.

b Day 1 is defined as the date of first treatment administration.

c Baseline data must be collected before time of study drug administration during Visit 2.

d Only measurements collected after drug administration at Visit 2a are considered Week 1 values.

e In case of premature treatment discontinuation FU starts at +1 day after last drug admin for these values.

Table 6.7: 3 Visit intervals for vital signs and laboratory data for patients from sites in Spain only

Interval Definition				
Visit	Planned day	From (day)	To (day)	Visit description
1	-28- -3	NA	-1	Screening
2a	1	1 ^a	1	Baseline ^b
2b	8	1 ^c	11	Week 1 (Day 8)
2c	15	12	22	Week 2 (Day 15)
3	29	23	40	Week 4 (Day 29)
3c	50	41	53	Week 6 (Day 50)
4a	57	54	70	Week 8 (Day 57)
4b	83	71	84	Week 11 (Day 83)
EOT	85	85	Date of drug intake in EOT visit +1	Week 12 (Day 85)
FU1		Date of drug intake in EOT visit +2	Date of drug intake in EOT visit +34	Follow-up 1 ^d
FU2		Date of drug intake in EOT visit +35	Date of drug intake in EOT visit +62	Follow-up 2
FU3		Date of drug intake in EOT visit +63	Last assessment date	Follow-up 3

a Day 1 is defined as the date of first treatment administration

b Baseline data must be collected before time of study drug administration during Visit 2.

c Measurements collected after drug administration at Visit 2a or at Visit 2b are considered Week 1 values.

d In case of premature treatment discontinuation FU starts at +1 day after last drug admin for these values.

[figure not shown]

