7.8 SAFETY ANALYSIS

Safety analyses will be performed on the treated set (TS).

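### SAP 7.8.4 leaves a treated patient with no baseline value for any ECG interval out of the ECG tables and the notable-finding listing, although SAP 6.6 says how to classify that patient

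*SAP*

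**What the plan says.** SAP 6.3 defines the ECG analysis set (ECGS) as one that "includes all subjects in TS who have at least one baseline and one post-baseline measurement for at least one ECG interval endpoint". SAP 7.8.4 opens with "All evaluations of ECG data will be based on data from the ECGS". Beneath that sentence stand the absolute-value summaries, the change-from-baseline summaries, the frequency tables for categorical and morphological findings, and this display: "For patients with any notable finding in quantitative ECG recordings, a separate listing with corresponding time profiles will be created".

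SAP 6.6 handles missing ECG baselines explicitly. One rule begins "If baseline is missing and the maximum on-treatment QTc interval is greater than 450 msec" (500 msec for uncorrected QT) and classifies the patient as new onset. Another reads "If baseline is missing, a QTc/QT interval > 500 msec at any time on treatment will be a notable finding".

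On the general safety population, Protocol 7.3.4 says "All treated patients will be included in the safety analysis", and SAP 7.8 opens by placing safety analyses on the treated set. Table 6.3: 1 gives ECG endpoints a row separate from safety endpoints.

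**The concern.** SAP 6.6 tells the programmer to classify and flag a patient whose baseline is missing. SAP 6.3 and 7.8.4 together remove that patient from every ECG evaluation if no interval has a baseline. For such a patient both instructions cannot be followed.

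A baseline is needed to compute a change, but not to see that a QTc exceeds 500 msec. Protocol 3.3.4.1 lists QTcF above 500 ms among its criteria for withdrawal from treatment, so the protocol itself treats that threshold as important. As written, a 7.8.4 frequency table or notable-finding listing could show no case above the threshold when the database holds one.

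**Working it through.** The plan states no figure on this point, so the check is one of set membership, followed by a small illustration.

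**Step 1: membership.** Take a treated patient with at least one post-baseline ECG and a maximum on-treatment QTc of 510 msec (an invented value). Apply SAP 6.3, then 6.6, then 7.8.4.

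| Baseline status | In ECGS (6.3)? | Class under 6.6 | In the 7.8.4 displays? |
|---|---|---|---|
| QTc baseline present | Yes | Missing-baseline rules not needed | Yes |
| QT/QTc baseline missing, but another interval (such as PR or QRS) has baseline and post-baseline values | Yes | New onset (510 > 450) and notable (510 > 500) | Yes |
| No baseline for any interval | No | New onset and notable | No |

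Only the third row is a conflict. In the second row the 6.6 rules work as intended.

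**Step 2: can a later ECG supply the baseline?** Not normally. A footnote to the visit-interval tables in SAP 6.7 says "Baseline ECG data are collected at screening visit". Protocol Flow Chart footnote 8 places treatment-period ECGs about 60 minutes after dosing, so the Visit 2a recording is post-dose.

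**Step 3: effect on a displayed count.** Assume an arm of 50 treated patients (the planned size, Protocol 7.7). One has QTc above 500 msec and no baseline for any interval. The other 49 are all in the ECGS and none exceeds 500 msec. Exact (Clopper-Pearson) 95% intervals:

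- ECGS: 0/49 = 0%. Upper limit 1 − 0.025^(1/49) = 0.0725, so 0 to 7.3%.
- Treated patients with an on-treatment ECG: 1/50 = 2.0%. Lower limit 1 − 0.975^(1/50) = 0.0005. The upper limit, from the beta quantile with parameters 2 and 49, is 0.1065. The interval is 0.05 to 10.6%.

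The intervals overlap almost entirely. What changes is that a zero becomes a non-zero count, and an entry appears in the notable-finding listing.

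**Step 4: how many patients?** The documents give no rate of missing baseline ECGs. Assumed rates of 0%, 1%, 2% and 5% of 100 patients put 0, 1, 2 and 5 outside the ECGS for lack of a baseline. These are upper bounds on the hidden threshold cases, since most such patients would not have a prolonged QTc.

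**The case against.** The strongest reply is that the group should be close to empty and that such a patient would be seen elsewhere. Much of this stands.

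- **Rarity.** The screening ECG is the baseline, exclusion criterion 13 needs a baseline QTcF, Protocol 6.2.1 makes randomization wait for ECG results, and Protocol 8.3.1 says missing records do not make a patient eligible. Protocol 5.2.4 calls for three recordings per time point and allows repeats for quality. The case should be rare, though the authors of SAP 6.6 thought it worth a rule.
- **Other routes.** A reader might infer that the value is lost from the report altogether. The documents do not support that. SAP 7 plans source listings of individual values for all patients, Protocol 7.3.4 has clinically relevant ECG findings reported as adverse events (analysed on the treated set), and Protocol 3.3.4.1 requires the reason for withdrawal from treatment to be recorded and reported. These routes rest on raw listings, investigator judgement or the withdrawal record. They do not replace the count and the listing that the SAP promises.
- **The 6.6 rules have a use.** A reader might infer that they are dead text. They are not: they apply whenever only the QT/QTc baseline is missing and another interval is complete.
- **An explicit exception.** Table 6.3: 1 and 7.8.4 set ECG endpoints apart, so the specific sentence can be read as overriding the general treated-set statement. That weakens the conflict with SAP 7.8 and Protocol 7.3.4, but not the conflict with SAP 6.6.

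Two further inferences fail. A patient with a baseline but no on-treatment ECG also falls outside the ECGS, but has no on-treatment value to report; showing that patient as missing or leaving the patient out is a matter of presentation. Nor can SAP section 4 be faulted for not announcing the restriction, because parts of it are redacted.

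**Conclusion.** The inconsistency is real and narrow. A treated patient with no baseline value for any ECG interval is classified by SAP 6.6 but left out of the 7.8.4 summary tables and notable-finding listing. This follows from the text alone. The size does not: it rests on an unknown frequency that should be low, and the 0/49 against 1/50 contrast uses assumed counts. ECG findings are descriptive and are neither the primary nor a secondary endpoint. The severity is minor. It merits correction because a stated safety rule cannot operate for some of the patients it describes, and the repair is nearly free.

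**What to change.** In SAP 7.8.4 and Table 6.3: 1, keep the ECGS for change-from-baseline summaries. Base the absolute values, the new-onset categories (with the 6.6 missing-baseline rules), the morphological findings and the notable-finding listing on treated patients with at least one on-treatment ECG.

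The cost is a few words in two places and one population flag, with no new data. Denominators may differ slightly between the change tables and the absolute-value tables, which a footnote can explain.

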7.8.5 Others

[figure not shown]

For future disclosure of trial results, specific data summaries will be included in the CTR or CTR appendices. Required displays will be specified in the technical TSAP.

10. HISTORY TABLE

Table 10: 1 History table

Version	Date (DD-MMM-YY)	Author	Sections changed	Brief description of change
1	29-JUN-2020	[REDACTED]	All	This is the final TSAP prior to DBL; based on initial TSAP approved 12- SEP-2017.
